**PRINCIPAL INVESTIGATOR: [name], PhD**

**ABSTRACT:**

Many people who receive a prescription for opioids report having leftover opioids once they are no longer needed to treat pain. These leftover opioids, which are rarely disposed of, can enable the opioid crisis by serving as a reservoir of drug available for misuse. For example, 90% of people who misuse prescription opioids report obtaining them from a family member or friend, or their own legitimate prescription. One way to reduce the amount of leftover opioids remaining in homes is to dispose of them once they are no longer needed. As a result, the Food and Drug Administration currently recommends that patients dispose of leftover prescription opioids by returning them to an authorized permanent collection site (e.g., medication drop boxes), or, when this is not feasible, flushing leftover opioid down the toilet. A newly available home disposal option involves use of a drug disposal kit. One such kit is DisposeRx. This product, which is available for purchase without a prescription, provides a safe and quick way to dispose of prescription medication. When a person mixes leftover drug with the DisposeRx powder and water, DisposeRx traps the medication in a gel which can then be safely disposed of in household trash. However, it is not known whether provision of drug disposal kits will increase the likelihood that leftover opioids will be disposed of by patients as compared to the currently accepted best practice, which is to provide instructions on how to safely dispose of leftover medications at home. This study will test the hypothesis that participants who receive a drug disposal kit such as DisposeRx will have the same rate of disposing of leftover prescription opioids as participants who are given standard instructions on how to dispose of leftover prescription opioids (i.e., currently accepted best practice). We will conduct a randomized controlled trial of individuals filling a new prescription for an opioid medication in the Johns Hopkins pharmacies to answer this question. Individuals will be called by telephone up to 6 weeks after they fill their prescription to determine whether or not they have disposed of their leftover prescription opioid medications, and if so by what means.

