Follow up telephone survey: Participants will be contacted by an IRB-approved member of the study team via telephone at 3 weeks after filling the opioid prescription and asked to complete a standardized survey. Up to three contacts via telephone will be attempted between 20 and 26 days after the prescription is filled. If the participant has not completed opioid therapy at that time or does not respond to any of the 3 phone calls, they will be contacted at 6 weeks to complete the survey. For these participants, up to three contacts via telephone will be attempted between 40 and 46 days after the prescription fill.

During data collection and with annual progress reports to the IRB, we will include counts of the number of subjects who decline to provide data at the week 3 and week 6 outcome assessments, and provide counts of the number of subjects, if any, who express displeasure with learning that they have been entered in a research study without their prior consent.

We are requesting a waiver for consent for the randomization to the disposal intervention portion of this study; however, when we call patients at 3 and/or 6 weeks later, we will ask them if they are willing to answer survey questions related to the disposal of their opioid medication/s. If they do not want to respond to any questions, we will not continue with the survey nor will we attempt to contact them again. If the patients indicate they are willing to answer the survey questions, then we will obtain oral consent for the survey portion of this study from participants at that time.

Study duration: Each participant will be asked to complete one 6-minute telephone survey at 3 weeks after the date of filling the opioid prescription. Participants who have not stopped using

opioids at 3 weeks or who did not respond to any of the 3 phone calls at 3 weeks will be asked to complete a follow-up telephone survey at 6 weeks after the date of filling the original opioid prescription. No additional study visits or interactions will be required. This study is expected to begin as soon as IRB approval is obtained and will last for approximately one year to include data analysis.

**Blinding:** Participants and researchers will be aware (i.e., not be blinded) to the Disposal Intervention. It is not feasible to blind either group to either Disposal Intervention.

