#### Exclusion Criteria

1. Age  $< 18$  years
2. Non-English speaking
3. Residential address and/or phone number unavailable or outside the United States
4. Opioid medication listed in participant's active medication list prior to prescription fill
5. Filling any prescription consisting of any opioid with 8 or more days' supply
6. Filling any prescription consisting of any extended-release / long-acting opioid medication (i.e., extended-release morphine, oxymorphone, oxycodone, hydromorphone, fentanyl, methadone, buprenorphine)

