## **Analysis Plan**

Sample size estimates: Sample size is calculated based on estimated effects on the primary outcome measure, the number of participants using a safe drug disposal method for leftover prescription opioids. This is defined as participants who report "yes" to disposing of leftover prescription opioid medication using a disposal intervention that aligns with recommendations from the Food and Drug Administration (i.e., using a take-back program, drug disposal kit, or flushing in the toilet) up to 6 weeks after prescription fill. At the time of writing this protocol, no published studies have examined the impact of disposal kits on rates of safe disposal of leftover prescription opioids. We estimate that the 'fact sheet' group will have a disposal rate of one in six patients (~17%), and that the 'drug disposal kit' group will have a disposal rate of one in three patients (~33%). To achieve 80% power with  $\alpha = 0.05$ , each group will require 126 patients. We will allocate patients 1:1:1 among the 'drug disposal kit' group, 'fact sheet' group, and 'control' groups, and thus require a sample size totaling 378 patients. Based on prior studies, we anticipate a dropout rate of 10-15%; allowing for a conservative non-response rate of 24.25%, we will need to enroll 499 participants.

We estimate that the 'no intervention' group (i.e., current standard of care) will have a disposal rate of 5%, based on previous studies of patients after surgery reporting disposal at 1 month. When we compare the 'no intervention' group with 'fact sheet' group, this sample will provide 82% power to detect a difference. When we compare the 'no intervention' group with the 'drug disposal kit' group, this sample will provide >99% power to detect a difference.

Primary analyses: We will use an intent-to-treat analysis approach, including all eligible patients in the group to which they were originally assigned. We will compare baseline characteristics and potential confounders between the three groups. Any imbalance will lead to additional analyses, as described in the "potential confounding" section below. The amount of opioids will be described as total morphine-equivalent mg using standard conversion tables from the CDC Guideline for Prescribing Opioids for Chronic Pain.

Aim 1: To compare disposal interventions on safe drug disposal up to 6 weeks after filling an opioid prescription.

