The primary outcome is the number of participants using a safe drug disposal method for leftover prescription opioids, as defined in the "sample size estimates." The primary comparison of interest is comparison of the 'drug disposal kit' group and the 'fact sheet' group. The secondary comparisons of interest are the comparisons of each of these two groups with the 'no intervention' group. Based on the study design and methods, we will examine outcomes for each individual at one point in time in follow up (i.e., 3 weeks or 6 weeks after filling at prescription). Thus, results from the 3-week follow up will be combined with results from the 6-week follow up for the purposes of statistical analyses. Additionally, the primary outcome of using a disposal intervention is only applicable for individuals who have completed their course of therapy. In other words, individuals who have not completed their course of opioid therapy would not be eligible to use a disposal intervention given they are still using their prescription opioid therapy. As a result, the primary outcome will be analyzed only in the subset of individuals who have reported that they have stopped taking prescription opioids at the time of follow up.

Preliminary analyses will use intent-to-treat analyses to compare the number of individuals reporting the use of a safe drug disposal method for leftover prescription opioids using chisquared tests to compare proportions. In an adjusted models for the primary analysis, we will use log-binomial regression to determine the risk ratio of safe drug disposal comparing two groups. We will conduct sensitivity analyses using Poisson models with robust error variance. We will present outcome measures with 95% confidence intervals and make no adjustment for multiple comparisons.

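### Do outcomes worded as up to 6 weeks need redefining when participants who have stopped opioids and answer at week 3 are not asked again?

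*Combined protocol and SAP*

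**What the plan says.** The Sample size estimates paragraph of the Analysis Plan defines the primary outcome. A participant counts if he or she reports having disposed of leftover opioids by a take-back programme, "drug disposal kit, or flushing in the toilet) up to 6 weeks after prescription fill". Aims 1 to 3 and the table of secondary outcomes (any disposal, safe storage, completion of therapy) carry the same time phrase.

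The schedule is in the Follow up telephone survey and Study duration paragraphs. The basic commitment is that "Each participant will be asked to complete one 6-minute telephone survey at 3 weeks after the date of filling the opioid prescription". A second round is conditional: if therapy is not complete at week 3, or the participant "does not respond to any of the 3 phone calls, they will be contacted at 6 weeks to complete the survey". For that group "up to three contacts via telephone will be attempted between 40 and 46 days after the prescription fill". Study duration adds that nothing further is asked of anyone.

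Aim 1 of the Analysis Plan then says how this is analysed: "we will examine outcomes for each individual at one point in time in follow up", and "results from the 3-week follow up will be combined with results from the 6-week follow up for the purposes of statistical analyses". It restricts the disposal analysis to people who report having stopped opioids by the time of the survey.

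Two other places bear on the reading. The Abstract uses the phrase for the calls themselves: "Individuals will be called by telephone up to 6 weeks after they fill their prescription". The Exclusion Criteria remove longer supplies ("Filling any prescription consisting of any opioid with 8 or more days" of supply), so every enrolled prescription covers 7 days or fewer.

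**The concern.** Read alone, the outcome definition promises that any disposal before week 6 will count. The schedule cannot deliver that. A person who has stopped, answers on day 20 with leftovers still in the house and disposes of them on day 30 is recorded as not having disposed. People in the same pooled proportion have been observed for quite different lengths of time.

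The time phrase also seems to work in two ways. A person who has not completed therapy at week 3 is asked again at week 6. A person who has stopped but not disposed is not.

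At stake would be the meaning of the absolute proportions, which the health system may use when it decides whether to supply kits. If anyone disposes after the week-3 call, a figure read as the 6-week proportion would be too low. Which window a person falls in depends on stopping opioids and answering the telephone, both of which happen after randomization. A difference in window mix or in speed of disposal between arms could therefore also shift the risk ratio.

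**Working it through.** **1. The plan's own figures.** Inputs from Sample size estimates: 17% (fact sheet), 33% (kit), alpha 0.05 (two-sided assumed), power 80%.

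- Uncorrected: n0 = [1.96·√(2·0.25·0.75) + 0.8416·√(0.17·0.83 + 0.33·0.67)]² / 0.16² = (1.2002 + 0.5065)² / 0.0256 = 113.8.
- With continuity correction: n = (n0/4)·[1 + √(1 + 4/(n0·0.16))]² = 126 per group, as stated.
- Enrolment: 3 × 126 = 378, and 378/(1 − 0.2425) = 499.0, as stated.

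The kit and fact-sheet rates are the investigators' estimates for the outcome as defined. The only rate with its own time base is the 5% for control, taken from studies reporting at 1 month. No stated figure is shown to be wrong by the timing of the survey.

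**2. Time not observed.**

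- Week-3 respondent, days missing before day 42: 42 − 26 = 16 to 42 − 20 = 22.
- Difference in observation time between the two windows: 40 − 26 = 14 to 46 − 20 = 26 days.
- Days from the nominal end of a 7-day supply to the week-3 call: 20 − 7 = 13 to 26 − 7 = 19. Shorter supplies leave longer.

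**3. Effect on an absolute proportion (assumed values).** Let w be the share of analysed people surveyed at days 40-46 and f the fraction of 6-week disposals already made by the week-3 survey. The captured fraction is c = w + (1 − w)f. The documents give neither w nor f. For a true 6-week rate of 30%:

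| f | w = 0.20 | w = 0.35 |
|---|---|---|
| 1.00 | c = 1.00, reads 30.0% | c = 1.00, reads 30.0% |
| 0.90 | c = 0.92, reads 27.6% | c = 0.935, reads 28.1% |
| 0.60 | c = 0.68, reads 20.4% | c = 0.74, reads 22.2% |

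**4. Effect on the comparison.** With the same c in both arms, RR = c·p1/(c·p0) = p1/p0 = 0.33/0.17 = 1.94, unchanged. It moves only if c differs by arm. With w = 0.30, f = 0.9 for kit and 0.7 for fact sheet gives 1.94 × 0.93/0.79 = 2.29; the reverse gives 1.94 × 0.79/0.93 = 1.65. Nothing in the documents suggests either pattern.

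**5. Effect on power.** If 17% and 33% were meant as full 6-week rates, w = 0.30 with f = 0.9 would give observed rates of 15.8% and 30.7%, and continuity-corrected power of 75.7% at 126 per group. With f = 0.6 the rates would be 12.2% and 23.8%, and power 60.2%. The plan does not call them cumulative 6-week rates. Rewording the outcome would not restore any power.

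**6. Definition against analysis text.** Aim 1 takes its outcome from the Sample size estimates paragraph and, in the same paragraph, fixes the timing: one survey per person, at 3 or 6 weeks, pooled. The definition counts people who report disposal, so it is a survey response with an outer time limit. The re-asking rule is also consistent. Aim 1 treats disposal as not applicable until therapy has ended, so those still on therapy must be called again before they can enter the disposal analysis. Those who have stopped already have an answer.

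**The case for a change.** The strongest case for a change is that outcome definitions travel further than analysis paragraphs. A report may carry the 6-week phrase into its abstract without the one-survey rule, and the definitions do not themselves say that the phrase means the survey the person happened to complete. Late disposal may be uncommon after so short a supply, but the documents do not show it. A clarifying clause and a count of survey window by arm would cost almost nothing.

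Most of this is true, and the description of the schedule stands. What does not stand is the step to a fault in the plan. A reader of Aim 1 is told exactly what is measured. The hypothesis in the Abstract and the Objectives speak of disposal without a 6-week endpoint. The analysis by window that might be added would condition on response and completion after randomization and could not recover a 6-week effect. A true 6-week proportion would need a second call to people who had stopped by week 3. The plan chose one completed assessment per person instead, which is a fair trade-off in a pragmatic telephone study.

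**Conclusion.** No change to the plan follows. The time phrase is loose when taken alone, but Aim 1 resolves it, and an analyst following Aim 1 would compute the same proportions and risk ratios under either wording. The sensible description is status reported at the completed 3- or 6-week survey among those who had stopped opioids. The plan already supplies what is needed to write that.

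The possible understatement of a 6-week proportion runs from none (f = 1.00) to about 2 percentage points (f = 0.90) and 8 to 10 points (f = 0.60) on a true 30%, using assumed values throughout. The kit versus fact sheet risk ratio is unaffected provided that window share and speed of disposal are alike in the arms. The documents give no evidence on that either way, and no bias is shown.

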### **INCLUSION/EXCLUSION CRITERIA:**

#### Inclusion Criteria

1. Adult participants (age  $\geq 18$  years) who pick up an opioid prescription for themselves or a family member at a Johns Hopkins pharmacy
2. English speaking
3. Residential address and phone number in the United States
4. Filling a new prescription consisting of an immediate release opioid medication (i.e., immediate release morphine, oxycodone, hydromorphone, hydrocodone, tramadol; alone or in combination with acetaminophen) with  $\leq 7$  days' supply

#### Exclusion Criteria

1. Age  $< 18$  years
2. Non-English speaking
3. Residential address and/or phone number unavailable or outside the United States
4. Opioid medication listed in participant's active medication list prior to prescription fill
5. Filling any prescription consisting of any opioid with 8 or more days' supply
6. Filling any prescription consisting of any extended-release / long-acting opioid medication (i.e., extended-release morphine, oxymorphone, oxycodone, hydromorphone, fentanyl, methadone, buprenorphine)

### **DISPOSAL INTERVENTIONS:**

This study will evaluate two Disposal Interventions: 1) the DisposeRx drug disposal kit with instructions on how to use DisposeRx and 2) an informational handout listing opioid disposal methods recommended by the Food and Drug Administration, along with the current standard of care of no Disposal Intervention.

The DisposeRx drug disposal kit was selected as the potential drug disposal system of choice for the Johns Hopkins Health System after a review process conducted by the Johns Hopkins Department of Pharmacy and the Johns Hopkins Opioid Stewardship Clinical Community. First, seven drug disposal systems or kits were assessed on various criteria. Five of those seven were selected for use in focus groups by frontline staff (15 physicians, nurses, and pharmacists at Johns Hopkins, which included study co-investigators) and patients (13 members from the Johns Hopkins Home Care Group Patient and Family Advisory Council). The top two products were then brought to the Johns Hopkins Opioid Stewardship Clinical Community for consideration. DisposeRx was selected as the potential preferred product due to ease of use. The DisposeRx

formulation is manufactured of components that are generally recognized as safe (GRAS) by the Food and Drug Administration; these substances are often included in various foods and drugs, and are not toxic. The desiccant silica powder is also listed by the FDA as a GRAS ingredient (GRAS Notice (GRN) No. 298:

<http://www.fda.gov/Food/FoodIngredientsPackaging/GenerallyRecognizedasSafeGRAS/GRASListings/default.htm>). In addition to providing the DisposeRx drug disposal kit, participants will be given an fact sheet or informational handout with instructions on how to use DisposeRx. This document was created in part by the Johns Hopkins Medicine Patient and Family Education and is a publicly available document at <http://johnshopkinsibportal.staywellsolutionsonline.com/Search/22,655>.

The fact sheet or informational handout lists information on the safe use of prescription opioids, including disposal methods recommended by the Food and Drug Administration. The paper document is a HealthSheet™, which is an evidence-based, peer-reviewed document written specifically for patients. These documents cover diseases and conditions, diagnoses and treatments, surgeries and procedures, and wellness and safety for people of all ages and walks of life. The main methods of drug disposal recommended on the handout and by the FDA include using medication take-back programs, which are available at select local and Hopkins pharmacies, or flushing leftover medication down the toilet. This document was created in part by the Johns Hopkins Medicine Patient and Family Education and has been hosted on the StayWell web portal at <http://johnshopkinsibportal.staywellsolutionsonline.com/Search/22,279>. This document incorporates recommendations from the Food and Drug Administration on how to dispose of leftover prescription opioid medications in a safe way.

Finally, the current standard of care in the Johns Hopkins Outpatient Pharmacies is for persons filling prescriptions to not receive written information from the pharmacy on the safe disposal of leftover prescription opioids upon filling a prescription for an immediate release opioid medication.

1. Centers for Disease Control and Prevention. *Multiple cause of death data on CDC WONDER*. Atlanta, GA: US Department of Health and Human Services, CDC, 2018.
2. Substance Abuse and Mental Health Services Administration. *Key Substance Use and Mental Health Indicators in the United States: Results from the 2017 National Survey on Drug Use and Health. Key substance use and mental health indicators in the United States: Results from the 2017 National Survey on Drug Use and Health*. Rockville, MD: Center for Behavioral Health Statistics and Quality, Substance Abuse and Mental Health Services Administration, 2018.

## **Analysis Plan**

Sample size estimates: Sample size is calculated based on estimated effects on the primary outcome measure, the number of participants using a safe drug disposal method for leftover prescription opioids. This is defined as participants who report "yes" to disposing of leftover prescription opioid medication using a disposal intervention that aligns with recommendations from the Food and Drug Administration (i.e., using a take-back program, drug disposal kit, or flushing in the toilet) up to 6 weeks after prescription fill. At the time of writing this protocol, no published studies have examined the impact of disposal kits on rates of safe disposal of leftover prescription opioids. We estimate that the 'fact sheet' group will have a disposal rate of one in six patients (~17%), and that the 'drug disposal kit' group will have a disposal rate of one in three patients (~33%). To achieve 80% power with  $\alpha = 0.05$ , each group will require 126 patients. We will allocate patients 1:1:1 among the 'drug disposal kit' group, 'fact sheet' group, and 'control' groups, and thus require a sample size totaling 378 patients. Based on prior studies, we anticipate a dropout rate of 10-15%; allowing for a conservative non-response rate of 24.25%, we will need to enroll 499 participants.

We estimate that the 'no intervention' group (i.e., current standard of care) will have a disposal rate of 5%, based on previous studies of patients after surgery reporting disposal at 1 month. When we compare the 'no intervention' group with 'fact sheet' group, this sample will provide 82% power to detect a difference. When we compare the 'no intervention' group with the 'drug disposal kit' group, this sample will provide >99% power to detect a difference.

Primary analyses: We will use an intent-to-treat analysis approach, including all eligible patients in the group to which they were originally assigned. We will compare baseline characteristics and potential confounders between the three groups. Any imbalance will lead to additional analyses, as described in the "potential confounding" section below. The amount of opioids will be described as total morphine-equivalent mg using standard conversion tables from the CDC Guideline for Prescribing Opioids for Chronic Pain.

Aim 1: To compare disposal interventions on safe drug disposal up to 6 weeks after filling an opioid prescription.

The primary outcome is the number of participants using a safe drug disposal method for leftover prescription opioids, as defined in the "sample size estimates." The primary comparison of interest is comparison of the 'drug disposal kit' group and the 'fact sheet' group. The secondary comparisons of interest are the comparisons of each of these two groups with the 'no intervention' group. Based on the study design and methods, we will examine outcomes for each individual at one point in time in follow up (i.e., 3 weeks or 6 weeks after filling at prescription). Thus, results from the 3-week follow up will be combined with results from the 6-week follow up for the purposes of statistical analyses. Additionally, the primary outcome of using a disposal intervention is only applicable for individuals who have completed their course of therapy. In other words, individuals who have not completed their course of opioid therapy would not be eligible to use a disposal intervention given they are still using their prescription opioid therapy. As a result, the primary outcome will be analyzed only in the subset of individuals who have reported that they have stopped taking prescription opioids at the time of follow up.

Preliminary analyses will use intent-to-treat analyses to compare the number of individuals reporting the use of a safe drug disposal method for leftover prescription opioids using chisquared tests to compare proportions. In an adjusted models for the primary analysis, we will use log-binomial regression to determine the risk ratio of safe drug disposal comparing two groups. We will conduct sensitivity analyses using Poisson models with robust error variance. We will present outcome measures with 95% confidence intervals and make no adjustment for multiple comparisons.

Missing data and potential confounding: We anticipate a low rate of missing data. Reasons for missing data will be recorded. We will compare observed outcomes at time points prior to dropout between the three groups. We do not plan on imputing missing data nor fitting complex models for missing data. We will examine groups to determine if potential confounding variables (e.g., amount of prescribed opioids in standardized morphine milligram equivalents, age, sex, etc.) are balanced. If they are not, we will conduct additional analyses to evaluate whether the findings are due, in part, to these imbalances. We will add potential confounders as covariates in models to adjust for them, and we will also examine for the potential effects of interactions between confounders and treatment groups by adding interaction terms to the models.

Secondary analyses:

Aim 2: To compare disposal interventions on secondary outcomes, including use of any disposal method, safe storage of prescription opioids, and completion of therapy up to 6 weeks after filling an opioid prescription.

The approach described above (log-binomial regression, with consideration of adjustment for potential confounders) will be used to analyze data for secondary outcomes. Using the same rationale as presented in Aim 1, the secondary outcome of use of any drug disposal method will be analyzed only in the subset of individuals who have reported that they have stopped taking prescription opioids at the time of follow up. The secondary outcome for safe storage and therapy completion will be analyzed in all individuals.

Secondary outcome	Description
Number of participants using any drug disposal method for leftover prescription opioids	Participants who report "yes" to disposing of leftover prescription opioid medication using any method up to 6 weeks after prescription fill
Number of participants with safe storage of prescription opioids	Participants who report "yes" to safely storing prescription opioid medication (i.e., in a locked location) up to 6 weeks after prescription fill
Number of participants who completed prescription opioid therapy	Participants who report "yes" to completing therapy for prescription opioid medication up to 6 weeks after prescription fill

Aim 3: To compare disposal interventions on safe drug disposal up to 6 weeks after filling an opioid prescription for pediatric vs. adult prescription recipients.

The approach described above (log-binomial regression, with consideration of adjustment for potential confounders) will be used to analyze data for safe drug disposal with model including an indicator variable based on the age of the individual for whom the prescription was written (0- <18 years of age vs.  $\geq$ 18 years of age). Using the same rationale as presented in Aim 1, the outcome of safe drug disposal will be analyzed only in the subset of individuals who have reported that they have stopped taking prescription opioids at the time of follow up.

For this study, no interim analyses will be conducted and no stopping rules will be included.
